## 2.1. Clinical study Justification

Previously published data has indicated that blood flow changes measured by the AneurysmFlow software predicted thrombosis accurately with commercialized Flow Diverting Stents (FDS). ([name] *et al.*, 2014) The purpose of the clinical study in this protocol is to investigate the ability of the intra-operative, intra-aneurysmal flow evaluation to assist with the treatment of intracranial aneurysms  $\geq 5\text{mm}$  using FDS.

The clinical hypothesis of this protocol to be tested is that by knowing the potential aneurysm occlusion rates by calculation of the MAFA ratio during a procedure, one might be able to adapt the therapeutic strategy intra-operatively to maximize the flow diverting effect for inducing complete aneurysm occlusions. Different strategies can be used to accelerate the aneurysm occlusion such as the addition of another stent layer or stent-assisted coiling with a jailed micro-catheter. Current treatment strategies are based on personal physician preferences or on subjective evaluation of aneurysm stagnation.

In this protocol, we propose to test a more quantitative assessment of the intra-aneurysmal flow, which may be able to support intra-operative clinical decisions which improve the occlusion rate of IA(s) after FDS treatment. Additionally, data collected in this proposed study will further expand the body of clinical knowledge concerning the relationship between blood flow metrics (including but not limited to the MAFA ratio) as determined by the AneurysmFlow software and clinical outcome in patients undergoing treatment for intracranial aneurysms with FDS.

## 3. OBJECTIVES AND HYPOTHESES

### 3.1. Primary objective

The primary objective of this clinical study is:

- To assess the prognostic value of the MAFA ratio for predicting full aneurysm occlusion 12 months after flow diverter placement.

### 3.2. Secondary objectives

The secondary objective are:

- To assess the prognostic value of the MAFA ratio for predicting full aneurysm occlusion 6 months after flow diverter placement.
- To determine optimal MAFA ratio threshold.
- To register (serious) adverse events (i.e. re-operations, ruptures and deaths).

### 3.3. Exploratory objectives

The exploratory objectives are:

- To evaluate the potential value of additional AneurysmFlow parameters for predicting full aneurysm occlusion 6 and 12 months after flow diverter placement.
- To evaluate the potential value of additional clinical variables to predict full aneurysm occlusion 6 and 12 months after flow diverter placement using multivariate logistic regression.

## 4. STUDY DESIGN

### 4.1. General

This is a prospectively planned, single arm, observational, multicenter cohort study to assess the prognostic value of the MAFA ratio for predicting full aneurysm occlusion 12 months after flow diverter placement.

A prospective observational multi-center study has been chosen to observe standard of care with the study device. The multi-center nature of the study will not only enable more efficient patient enrollment and thus a

Philips IGT Systems  Status: Approved	Post-Market Clinical Study Plan  CARO A multicenter observational cohort study	XCY610-130253 2018 Apr 06 Revision: 2.0 Page 12 of 23
--	---	--

shorter study duration, but it will also provide information on heterogeneity between centers and enable (cross) validation of study results.

## 4.2. Study device exposure

This is an observational study, in which data is collected during the regular clinical procedure: a treatment of an aneurysm with (a) flow diverter(s). During this procedure, high-speed angiograms will be made before and after placement of the flow diverter device. Clinical decision making is not affected by this study.

There are no additional devices or medications required for the study.

## 4.3. Subjects

### 4.3.1. In- and exclusion criteria

Subjects participating in the study will be carefully selected based on the next inclusion and exclusion criteria.

#### 4.3.1.1. Inclusion criteria

- Subject with unruptured,  $\geq 5$ mm saccular aneurysm(s) located in the anterior intracranial circulation and suitable for an endovascular treatment with a Flow Diverter Stent
- Subject is 18 years of age or older, or of legal age to give informed consent per state or national law
- Subject is available for clinical follow-ups

#### 4.3.1.2. Exclusion criteria

- Non-saccular brain aneurysm(s) (i.e., dissecting, fusiform, atherosclerotic, mycotic, bifurcational) Prior aneurysm treatment with either endovascular (stenting, coiling) or surgical (clipping) techniques
- Endovascular treatment assisted with coils or intracranial stents
- Significant or severe allergy to intra-arterial contrast medium uncontrolled by pre-procedure medications
- Severe kidney disease (e-GFR < 60)
- Subjects not willing (or able) to attend post FDS insertion standard-of-care follow up clinic visits requiring DSA, head MRI or CTA imaging
- Subject participates in a potentially confounding drug or device trial during the course of the study.
- Subject meets an exclusion criteria according to national law (e.g. age, pregnant woman, breast feeding woman)

### 4.3.2. Enrollment and duration

Subjects are considered to be enrolled in the study after they have signed the informed consent form. The subjects will be followed-up at 6 and 12 months according to regular clinical standard of care.

The total duration of the study is expected to take approximately 2.5 years. Patient enrollment will take place between March 2018 and September 2019. Each subject will be in the study for 1 year (follow-up).

### 4.3.3. Number of subjects

In total 120 subjects will be enrolled in the study. The enrollment period is expected to last for 1 year.

See section 5 Statistical considerations for more details on the number of subjects.

### 4.3.4. Subject withdrawal or discontinuation

Subjects can withdraw informed consent at any time during the clinical investigation. There are no specific criteria for subject withdrawal or discontinuation.

Philips IGT Systems  Status: Approved	Post-Market Clinical Study Plan  CARO A multicenter observational cohort study	XCY610-130253 2018 Apr 06 Revision: 2.0 Page 13 of 23
--	---	--

#### 4.4. Procedures

Physician investigators participating in this study are expected to follow their normal clinical practice in enrolling, treating and following patients with intracranial aneurysms that are amenable to treatment with flow diverter stents. No additional procedures are required of patients in order to participate in this observational study.

##### Pre-Screening

Patients presenting with intracranial saccular aneurysm(s) will be evaluated by the neuro interventional team, in accordance with institutional practice, to establish an appropriate treatment plan based on the patient's medical condition and available diagnostic screening procedures prior to recruitment in the study. More than one aneurysm in a single patient may be treated, but only the target aneurysm(s) treated with FDS devices initially will be considered as part of this study. If treatment of the aneurysm with the FDS is deemed appropriate, the institution's guidelines regarding their ethics committee and informed consent process will be followed.

##### Screening

After obtaining the consent form(s) approved by the local research ethics board (REB), the principal investigator will screen the potential investigation subjects for the CARO study. The principal investigator or his delegates on the study team will enter data in a pre-designed e-CRF. This will include patient demographics, relevant past medical and surgical history, and specific target aneurysm data along with pre-procedural/screening imaging details.

Only patients who meet all inclusion and none of the exclusion criteria will qualify for this study. The measurement and size of each aneurysm will be verified by the principal investigator. If the size of the aneurysm is acceptable, then it will be included in the study. It is recommended that this measurement should be done within 180 days before the procedure.

[figure not shown]
##### Index Procedure and Discharge

The investigator will proceed with standard of care procedures on the day of Index Procedure (i.e. FDS insertion) for the target aneurysm(s). Then, endovascular treatment procedure details should be provided under the "INDEX PROCEDURE & DISCHARGE" field for each eligible patient.

Blood flow velocity will be calculated using the dedicated software AneurysmFlow (Philips Healthcare, Best, The Netherlands), which will be installed on standard of care imaging equipment. For this purpose, digital subtraction angiograms will be acquired during the procedure; just before and right after placement of the FDS.

Calculation of blood flow velocity will be performed automatically on the AneurysmFlow software. The operator will have access to the results of the calculation in addition to all of the regular information that is at his/her disposal during routine clinical practice. There are no additional devices or medications required for the study. The AneurysmFlow software uses standard-of-care 2D DSA and 3D-RA image sequences to determine this flow information. All raw image sequences will be stored for future reference.

Figure 1 shows the workflow for using the AneurysmFlow software in this study.

In step 1 a 3D rotational angiogram (3D-RA) will be performed in the neuro-interventional suite with the x-ray C-arm to acquire a 3D image volume of the aneurysm anatomy to be treated. From this 3D-RA, an optimal viewing angle for the C-arm will be determined to obtain good flow information. This angle should show the parent artery, aneurysm neck and aneurysm itself clearly without any overlap. The 3D-RA will also help to determine a good C-arm viewing angle to help position and deploy the FDS across the aneurysm.

In Step 2 a 2D DSA x-ray run with contrast agent injection (i.e. advised injection rate 1.5 to 2 cc/s) will be acquired at the optimal C-arm viewing angle determined by the 3D-RA scan to obtain dynamic blood motion information before FDS deployment at the location of the aneurysm. If the initial contrast agent injection was insufficient, the injection will be altered and repeated with another DSA run to obtain high quality image information. The FDS will then be placed at the location of the aneurysm.

In Step 3, after FDS deployment, a second DSA run with contrast agent will be acquired (i.e. injection rate  $\approx$ 1.5 to 2 cc/s) at the optimal C-arm viewing angle determined from the 3D-RA to qualitatively evaluate blood motion in the region of the aneurysm after deployment of the FDS. The C-arm angle and injection rate of this second DSA run (post FDS deployment) must be the same as the first DSA run (pre FDS deployment). The 2 DSA runs and the 3D-RA image volume will automatically be sent to the AneurysmFlow workstation right after they are acquired. If the FDS is ballooned after placement, the physician is asked to repeat Step 3 after ballooning.

In Step 4 a routine VasoCT scan, which is another 3D rotational x-ray C-arm scan, will then be performed with the x-ray C-arm in the neuro-interventional suite to evaluate the 3D apposition of the deployed FDS with respect the vessel wall.

The region of interest around the aneurysm and the corresponding arterial segment from which it has developed will be automatically segmented by the AneurysmFlow software, but manual controls are available in the software if modifications to the anatomical segment of interest are desired by the interventionalist. These modifications can be performed by an appropriately trained study member. The software will then automatically calculate the flow parameters of the aneurysm both before and after FDS deployment, along with the MAFA ratio.

For this study, the operator will have the choice of selecting which target aneurysms are amenable to FDS treatment. Patients that have single or multiple target aneurysms that are suitable for FDS treatment as a first treatment step would be acceptable for this study. Each target aneurysm in the patient will have a separate CRF sub-form to fill out. Additionally, each target aneurysm sub-form can be further divided into several FDS sub-forms to account for multiple flow diverters, if needed. To summarize, if the patient has more than one target aneurysm and/or needs more than one flow diverter per aneurysm, then a sub-form on the CRF will need to be filled out for each aneurysm and for each FDS used.

As shown in Figure 1, if a target aneurysm is treated with a FDS (or more than one) initially, and is then treated using another approach (such as coiling) then this target aneurysm can remain included as part of the study. However, if a target aneurysm is treated using a non-FDS approach initially (such as with coiling), followed by placement of an FDS or other approach, then the aneurysm will be excluded from the study.

Philips IGT Systems  Status: Approved	Post-Market Clinical Study Plan  CARO  A multicenter observational cohort study	XCY610-130253 2018 Apr 06 Revision: 2.0 Page 15 of 23
--	---	--

The MAFA ratio will be calculated after the placement of each FDS. For each FDS, this ratio will be determined with the flow information before any stents were placed and also with the flow information after each FDS was placed. The final MAFA ratio will be calculated using the flow information before any FDS devices were placed and using the flow information after the last FDS was placed. Clinical and imaging outcomes of a procedure will be assessed using a combination of the flow metrics calculated by the AneurysmFlow software available to the operator during interventional treatment in addition to information that is routinely acquired during FDS placement. This information acquired across the patient population in the study will also contribute to determine more precise MAFA ratio thresholds to improve prediction of complete aneurysm occlusion after FDS placement. This study will not make any recommendation on patient management or on treatment strategy. Also, this software will not disrupt standard-of-care workflow for the interventionalist.

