### 5.1. Sample Size Justification

The total sample size for this study was calculated using the following formulas for Receiver Operating Characteristics Studies (Obuchowski, 2000):

$$n_D = \frac{[z_\alpha \sqrt{0.0792 \times (1 + 1/\kappa)} + z_\beta \sqrt{V(\theta)}]^2}{(\theta - 0.5)^2}$$

where  $V(\theta)$  is the variance function of  $\theta$ , given by:

$$V(\theta) = (0.0099 \times e^{-A^2/2}) \times ([5A^2 + 8] + [A^2 + 8]/\kappa)$$

i.e., the variance of  $\theta$  is equal to  $V(\theta)/n_D$ ;  $A = \Phi^{-1}(\theta) \times 1.414$ ;  $\Phi^{-1}$  is the inverse of the cumulative normal distribution function;  $\kappa$  is the ratio of the number of control patients ( $n_C$ ) to the number of diseased patients ( $n_D$ ) in the study sample (i.e.,  $\kappa = n_C/n_D$ );  $\theta$  is the conjectured area under the ROC curve (under the alternative hypothesis);  $z_\alpha$  is the upper  $\alpha$ th percentile of the standard normal distribution, where  $\alpha$  is the type I error rate (usually  $\alpha = 0.05$ ); and  $z_\beta$  is the upper  $\beta$ th percentile of the standard normal distribution, where  $\beta$  is the type II error rate (often  $\beta = 0.10$  or 0.20).

Assuming  $\kappa=0.25$  (i.e., 4 times as many occluded aneurysms than non-occluded aneurysms after 1 year), a fair AUC of 0.70, a type I error of 0.05 and a type II error rate of  $\leq 0.10$  (power  $\geq 0.90$ ), a total of 100 subjects should be included in the study. This total number of 100 subjects also accommodates the pre-planned explorative multivariate analysis allowing inclusion of 8 candidate predictors including AneurysmFlow (Peduz *et al.*, 1996). Allowing for an expected drop-out rate of 15% we aim to include a total of 120 patients into the study.

Any deviation from the planned analysis described below will be documented with justification in the final clinical end report.

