### 5.2. General Consideration

The primary analysis of the prognostic value of the MAFA ratio for predicting full aneurysm occlusion 12 months after flow diverter placement will be performed including all subjects who underwent treatment. Baseline patient characteristics and follow-up results will be summarized descriptively using frequencies and percentages or summary statistics like means and medians (including confidence intervals and interquartile ranges). Multiple imputation methods will be used to correct for missing data (Rubin, 1987). All statistical analysis will be performed using R statistical software ([www.r-project.org](http://www.r-project.org))

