#### Endpoint

Philips IGT Systems  Status: Approved	Post-Market Clinical Study Plan  CARO A multicenter observational cohort study	XCY610-130253 2018 Apr 06 Revision: 2.0 Page 17 of 23
--	---	--

The primary endpoint is the prognostic value (i.e. c-statistic including confidence intervals) of the MAFA ratio with respect to full aneurysm occlusion (i.e. Raymond-Roy Occlusion Classification I (Roy *et al.*, 1997) on standard-of-care head imaging) 12 months after flow diverter placement.

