#### Experimental design

We will use logistic regression analysis to evaluate the univariate predictive association between the index test (i.e. the MAFA ratio) and complete aneurysm occlusion (i.e. complete occlusion yes/no) at 12 months (Moons *et al.*, 2012). All subjects with complete follow-up will be included in this analysis.

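### Patients may contribute several target aneurysms, but the plan defines no unit of analysis and no method for within-patient correlation; if aneurysms are pooled, the c-statistic interval may be modestly too narrow.

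*Combined protocol and SAP*

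**What the plan says.** **Eligibility and data capture (section 4.4).** Several aneurysms per patient are allowed, with no maximum: "Patients that have single or multiple target aneurysms that are suitable for FDS treatment as a first treatment step would be acceptable for this study". Under Index Procedure and Discharge, "Each target aneurysm in the patient will have a separate CRF sub-form to fill out". Inclusion is also decided per aneurysm. Under Screening, an aneurysm of acceptable size enters the study. Under Index Procedure and Discharge, a target aneurysm stays in or drops out according to how it was first treated.

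**Endpoint and method (section 5.4).** "The primary endpoint is the prognostic value (i.e. c-statistic including confidence intervals) of the MAFA ratio with respect to full aneurysm occlusion" at 12 months. The method is: "We will use logistic regression analysis to evaluate the univariate predictive association between the index test (i.e. the MAFA ratio) and complete aneurysm occlusion". The analysis set is worded in subjects: "All subjects with complete follow-up will be included in this analysis". Section 5.5.1 repeats this for 6 months. Section 5.2 also counts subjects; the primary analysis "will be performed including all subjects who underwent treatment".

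**Sample size (section 5.1).** The class ratio is worded in aneurysms, "4 times as many occluded aneurysms than non-occluded aneurysms after 1 year", but the totals of 100 and 120 are worded in subjects and patients.

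Nowhere does the plan name a unit of analysis, a rule for choosing one aneurysm per patient, a patient-level definition of MAFA ratio or occlusion, or a clustered variance, GEE, mixed model or patient-level resampling. The bootstrap in section 5.6.2 has no stated resampling unit.

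**The concern.** Two aneurysms in one patient share a host. The plan describes a single index procedure day for the target aneurysm or aneurysms and follow-up head imaging of the patient, and it lists medication as a candidate predictor of occlusion. Positive correlation is therefore plausible. The usual variance of a c-statistic assumes independent records. Applied to pooled aneurysms, it can understate the standard error of the primary endpoint, which is itself a c-statistic with its interval.

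The one-record-per-patient alternative cannot be carried out as written, because no selection rule is given. A choice made after occlusion is known would open the primary endpoint to selection. Either reading needs a rule that the plan does not contain.

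**Working it through.** **1. Reproduce the planned size.** Inputs from section 5.1: "a fair AUC of 0.70, a type I error of 0.05 and a type II error rate of" at most 0.10, with kappa = 0.25.

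- A = 0.5244 × 1.414 = 0.7415, so A² = 0.5498.
- V = 0.0099 × e^(−0.2749) × [(5 × 0.5498 + 8) + (0.5498 + 8)/0.25] = 0.00752 × 44.95 = 0.338.
- n_D = [1.645 × √(0.0792 × 5) + 1.2816 × √0.338]² / 0.2² = 79.23 with a one-sided alpha of 0.05.
- Total = 79.23 × 1.25 = 99.03, rounded up by class to 80 + 20 = 100. Power at 100 is 0.903.
- Drop-out: 100/0.85 = 118, against the plan's 120.

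The figure of 100 reproduces. The formula has no clustering term. At 100 independent units the standard error of the c-statistic is √(0.338/80) = 0.065, a 95% half-width of 0.127.

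**2. Simulate pooled aneurysms.** Setting: 100 patients, true AUC 0.70, 80% occluded, a binormal model, and a share of patients with exactly two aneurysms. The same within-patient correlation is applied to the MAFA ratio and to occlusion. Share and correlation are assumptions. There were 12,000 runs per cell. Entries are the true standard error divided by the mean DeLong standard error that assumes independence, with coverage of the nominal 95% interval in brackets.

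| Patients with two aneurysms | Correlation 0.3 | 0.5 | 0.8 |
|---|---|---|---|
| 10% | 1.01 (0.934) | 1.02 (0.931) | 1.05 (0.924) |
| 20% | 1.02 (0.931) | 1.03 (0.930) | 1.07 (0.919) |
| 30% | 1.01 (0.938) | 1.03 (0.935) | 1.10 (0.912) |

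Monte Carlo error on a ratio is about 1/√(2 × 12,000) = 0.006, so the cells at correlation 0.3 are hard to tell from no effect. Without clustering (3,000 runs) the ratio was 0.98 and coverage 0.934. In the worst cell the naive half-width is 1.96 × 0.0572 = 0.112, where 1.96 × 0.0627 = 0.123 is needed.

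A second simulation, with 102 patients and 2,500 runs per setting, agrees. Its naive standard error is 2-9% too small at correlations of 0.5-0.8, with worst coverage 0.914 against 0.937 without clustering.

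**3. Both quantities must be correlated.** With correlation 0.5 in only the MAFA ratio or only occlusion (3,000 runs), the ratio was 0.99-1.02, which is no material narrowing.

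**4. Design-effect check.** With DE = 1 + (E[m²]/E[m] − 1) × rho and m aneurysms per patient, a 30% share gives E[m] = 1.3 and E[m²] = 1.9. At rho = 1, DE = 1.462 and the interval factor is √1.462 = 1.21. This is an upper bound for a 30% share.

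**5. Effective size when 100 counts patients.** Effective units = 100 × E[m]/DE.

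| Share | rho 0.5 | rho 0.8 |
|---|---|---|
| 10% | 110/1.091 = 100.8 | 110/1.145 = 96.0 |
| 20% | 120/1.167 = 102.9 | 120/1.267 = 94.7 |
| 30% | 130/1.231 = 105.6 | 130/1.369 = 94.9 |

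About 95 effective units give a one-sided power of about 0.89, against 0.903.

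**The case against.** The strongest reply is that the plan never says aneurysms are pooled or treated as independent. Its analysis text counts subjects throughout, and the sub-form instruction concerns data capture. If one record per patient is meant, the effect is zero. It is also not stated how follow-up occlusion is recorded when a patient has several targets. All of this stands, and it rules out three stronger readings that a reader might infer.

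- *The plan treats all units as independent.* This is an inference from silence. What the documents show is an undefined unit and no named method.
- *The interval will be too narrow.* That needs pooling without adjustment, enough multi-aneurysm patients, and positive correlation in both the MAFA ratio and occlusion. None of these is given.
- *The sample size is inflated.* The totals are in subjects, so second aneurysms come on top of them. Step 5 shows planned power nearly intact. Larger losses arise only if 100 is taken to count aneurysms; for example, power is 0.857 at a 20% share and rho 0.5.

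The fix is also only a partial cure for coverage. In the worst cell a clustered variance raises it from 0.912 to 0.928, against about 0.934 without clustering. The remaining shortfall from 0.95 is a small-sample effect that clustering did not cause.

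The subject wording does not close the gap, however. Inclusion, predictor and outcome are all defined per aneurysm, and the one-per-patient reading lacks the rule needed to apply it.

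**Conclusion.** The point holds in a limited, conditional form. Several aneurysms per patient are allowed and entered separately, yet the primary and 6-month analyses define no unit and no handling of within-patient correlation. If aneurysm records are pooled under the named methods, the 12-month interval should be about 0-10% wider, and coverage falls from about 0.93 to 0.91 at worst. This rests on assumed shares of 10-30% with exactly two aneurysms and correlations of 0.3-0.8. The size at 6 months was not computed separately, because the plan gives no 6-month occlusion rate. The effect is zero with one aneurysm per patient. It is modest, but it concerns the error bars of the primary endpoint and should be settled before analysis.

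**What to change.** - **Sections 5.4 and 5.5.1:** state that the target aneurysm is the unit of analysis, and compute the c-statistic interval with a clustered-ROC variance or a bootstrap that resamples patients. Alternatively, pre-specify one index aneurysm per patient, with a selection rule fixed before outcomes are known. That could be the primary analysis, or a sensitivity analysis beside the clustered one.
- **Section 5.6.2:** resample patients, not aneurysms, in the bootstrap.
- **Section 5.1:** state that 100 and 120 count patients.

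Patient-clustered robust standard errors for the logistic coefficient are reasonable but do not change the c-statistic interval, so they cannot replace the first item.

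The cost is a few lines of text and a standard R routine. The index-procedure sub-forms already separate the aneurysms; it should be confirmed that follow-up occlusion is entered per aneurysm too. The interval becomes slightly wider: in the worst cell the half-width goes from 0.112 to 1.96 × 0.0613 = 0.120. The index-aneurysm option instead discards the additional aneurysms.
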